4.4 Randomization and Blinding

Participants confirmed to meet all eligibility criteria who have provided informed consent are randomized 1:1 to hydroxychloroquine versus placebo. A randomization code is provided to the site investigator or

delegate from a centralized, web-based platform. Randomization is completed in permuted blocks of varying size and stratified by site. The participant, treating clinicians, study personnel, and outcome assessors all remain blinded to group assignment until after the database is locked.

5. STUDY INTERVENTIONS

5.1 Hydroxychloroquine Group

Participants assigned to the hydroxychloroquine group receive hydroxychloroquine sulfate 400 mg enterally twice daily for the first two doses and then 200 mg twice daily for the subsequent eight doses. This dosing regimen is a total of 10 doses over 5 days with an 800 mg load in the first 24 hours divided into two doses followed by 400 mg daily divided into two doses over the following 4 days.

5.2 Control Group

Participants randomized to the control group receive matching placebo enterally twice daily matching the dosing regimen described above for hydroxychloroquine.

6. OUTCOMES

6.1 Primary Outcome

COVID Ordinal Outcomes Scale on Study Day 15:

1. Death
2. Hospitalized on invasive mechanical ventilation or ECMO
3. Hospitalized on non-invasive ventilation or high flow nasal cannula
4. Hospitalized on supplemental oxygen
5. Hospitalized not on supplemental oxygen
6. Not hospitalized with limitation in activity
7. Not hospitalized without limitation in activity

6.2 Secondary Outcomes

- Time to recovery, defined as time to reaching level 5, 6, or 7 on the COVID Outcomes Scale, which is the time to the earlier of final liberation from supplemental oxygen or hospital discharge
- All-location, all-cause 14-day mortality (assessed on Study Day 15)
- All-location, all-cause 28-day mortality (assessed on Study Day 29)
- Survival through Day 28
- Hospital discharge through Day 28
- COVID Ordinal Outcomes Scale on Study Day 3
- COVID Ordinal Outcomes Scale on Study Day 8
- COVID Ordinal Outcomes Scale on Study Day 29
- Composite of death or receipt of ECMO through Day 28
- Oxygen-free days through Day 28
- Ventilator-free days through Day 28
- Vasopressor-free days through Day 28

- ICU-free days through Day 28
- Hospital-free days through Day 28

6.3 Safety Outcomes

- Seizure
- Atrial or ventricular arrhythmia
- Cardiac arrest
- Elevation in aspartate aminotransferase or alanine aminotransferase to twice the local upper limit of normal
- Acute pancreatitis
- Acute kidney injury
- Receipt of renal replacement therapy
- Symptomatic hypoglycemia
- Neutropenia, lymphopenia, anemia, or thrombocytopenia
- Severe dermatologic reaction

7. DATA ANALYSIS PLAN

7.1 Trial Population

The primary population for analysis will be all patients enrolled in the trial. The primary approach to analysis will be by intention to treat, in which patients assigned to the hydroxychloroquine group are analyzed in the hydroxychloroquine group and patients assigned to the placebo group are analyzed in the placebo group, regardless of treatments received. All analyses will be intention-to-treat analyses among all enrolled patients unless otherwise specified.

7.2 Primary Analysis of the Primary Outcome

The primary outcome is patient clinical status 14 days after randomization (on Study Day 15) as assessed with a seven-category ordinal scale (the COVID Ordinal Outcome Scale). The scale consists of the following categories: 1, death; 2, hospitalized, receiving ECMO, invasive mechanical ventilation, or both; 3, hospitalized, receiving noninvasive mechanical ventilation, nasal high-flow oxygen therapy, or both; 4, hospitalized, receiving supplemental oxygen; 5, hospitalized, not receiving supplemental oxygen; 6, not hospitalized, but unable to perform normal activities; 7, not hospitalized, able to perform normal activities.

The primary analysis will be a comparison of the primary outcome between patients randomized to the hydroxychloroquine group versus the placebo group. The comparison will be made using proportional odds regression. The dependent variable will be the primary outcome. Independent variables will include treatment group assignment and the following pre-specified 5 covariates:

- Age at randomization
- Sex
- Clinical status as assessed by the COVID Ordinal Outcome Scale at randomization
- Sequential Organ Failure Assessment (SOFA) score at randomization
- Duration of acute respiratory infection symptoms prior to randomization

The placebo group serves as the referent group for analyses. Because the primary outcome ranges from “death” as the lowest value of 1 to “not hospitalized and without limitations in activities” as the highest value of 7, an odds ratio >1.0 indicates more favorable outcomes with hydroxychloroquine while an odds ratio <1.0 indicates more favorable outcomes with placebo. Results of the primary analysis of the primary outcome will be presented as an adjusted common odds ratio and associated 95% confidence intervals.

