3.7 Randomization and Blinding

Participants confirmed to meet all eligibility criteria who have provided informed consent will be randomized 1:1 to hydroxychloroquine versus placebo. A randomization code will be provided to the site investigator or delegate from a centralized, web-based platform. Randomization will require provision of the screening number and confirmation of patient eligibility.

Randomization will be completed in permuted blocks of varying size and stratified by site. The randomized sequence allocation will be stored on a secure server and will not be available to site study personnel. Site research personnel will have a unique Personal Identification Number (PIN) to access the

randomization system. Each subject will receive a computer-generated randomization ID number. The computer-generated randomization ID number will be provided to the pharmacy who will provide a dose pack containing hydroxychloroquine or placebo. The participant, treating clinicians, study personnel, and outcome assessors will all remain blinded to group assignment until after the database is locked and blinded analysis is completed.

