7. STATISTICAL CONSIDERATIONS

7.1 Statistical Approach

The primary analysis will be an intention-to-treat comparison of the Day 15 COVID Ordinal Outcome score between patients randomized to hydroxychloroquine versus placebo. This analysis will be conducted with a proportional odds model using the Day 15 COVID Ordinal Outcome score as the dependent variable, randomized group assignment as the primary independent variable, and the following co-variables: age, sex, baseline COVID Ordinal Outcome score, baseline SOFA score, and duration of acute respiratory infection symptoms prior to randomization. An odds ratio >1.0 indicates more favorable outcomes with hydroxychloroquine on the COVID Ordinal Outcome scale, while an odds ratio <1.0 indicates more favorable outcomes with placebo.

Patients enrolled prior to implementation of protocol version 2.0 who did not have laboratory confirmed SARS-CoV-2 infection will be included in the primary intention to treat analysis. In addition to reporting data for the full trial population we will also report data separately for patients randomized in the ICU (who tend to be more severely ill) and those randomized outside the ICU (who tend to be less severely ill) as well as those with duration of symptoms ≤ 5 days prior to randomization and those with >5 days of symptoms prior to randomization.

The anticipated study size is about 510 patients. We calculated the sample size under the assumption that we would have an interim analysis after approximately each 102 patients. We calculated the standard error of the log(odds-ratio) statistic with 51 patients per arm based on data from a recently completed trial within the PETAL Network that enrolled patients early in the course of critical illness, the *Vitamin D to Improve Outcomes by Leveraging Early Treatment* (VIOLET) trial.³⁵ In the VIOLET trial at Day 15, 11.5% of patients had died, 5.8% were on invasive mechanical ventilation, 22.9% remained in the hospital, and the remaining had been discharged from the hospital (Table 1). We used these outcomes in VIOLET to approximate Day 15 outcomes on the COVID Ordinal Outcome scale that we may observe in this trial.

Patient Status	Percentage of patients
Dead	11.5%
Invasive mechanical ventilation	5.8%
Hospitalized, not on invasive mechanical ventilation	21.9%
Discharged from the hospital	60.8%

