7.3 Sensitivity Analyses of the Primary Outcome

We will conduct two sensitivity analyses:

1. **Exclusion of SARS-CoV-2 negative patients.** The primary analysis included all enrolled patients enrolled in the trial. Given delays in SARS-CoV-2 testing early in the pandemic, the trial eligibility criteria initially allowed enrollment of hospitalized patients with suspected or confirmed SARS-CoV-2 infection. As testing capabilities improved, the inclusion criteria were narrowed on April 21, 2020 (after 18 days of enrollment and inclusion of 2 patients without laboratory-confirmed COVID-19) to include only laboratory-confirmed cases. To determine whether the results of the primary analysis of the primary outcome were affected by enrollment of patients who subsequently tested negative for SARS-CoV-2, in this sensitivity analysis the primary analysis will be repeated in the subset of patients with a positive test for SARS-CoV-2 (i.e., excluding patients without laboratory-confirmed SARS-CoV-2).
2. **Modified intention-to-treat.** The primary analysis will be repeated among the subset of patients who received at least one dose of study drug (excluding patients who received no doses of study drug).

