7.5 Analysis of Secondary and Safety Outcomes

Ordinal secondary will be analyzed using a proportional odds model with randomized group assignment as an independent variable and the covariables used in the primary model. Binary secondary outcomes will be analyzed using multivariable logistic regression models with the same pre-specified covariates. Survival and hospital discharge through day 28 will be analyzed using multivariable proportional hazards regression with the same covariates in the primary outcome model. For the hospital discharge model, death will be treated as a competing risk, and the sub-distribution hazard ratio will be reported.⁶ Safety outcomes will be analyzed with simple logistic regression without co-variable adjustment.

Detailed data on receipt of invasive mechanical ventilation, vasopressors, intensive care unit admission, and hospitalization were collected during the index hospitalization, but not after discharge from the index hospitalization. Therefore, the main analysis of the associated “-free day” outcomes will use information regarding receipt of the supportive therapy between randomization and hospital discharge or Study Day 29, whichever occurs first (“in-hospital outcome”). Information on death between discharge from the index hospitalization and Study Day 29 is systematically available via follow-up phone calls. Hence, we will use all-cause, all-location death in the calculation of “-free day” outcomes.

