Appendix A. Outcome variables by ORCHID Use, Type, and Analysis Method.

Variable	ORCHID Use	Type	Analysis Method
Clinical status 14 days after randomization as assessed with a seven-category ordinal scale (COVID Ordinal Outcomes Scale on Study Day 15)	Primary Outcome	Ordinal	Proportional odds model accounting for pre-specified baseline covariates
Time to recovery	Secondary Outcome	Continuous	Proportional odds model accounting for pre-specified baseline covariates
All-location, all-cause 14-day mortality (Study Day 15)	Secondary Outcome	Binary	Logistic regression model accounting for pre-specified baseline covariates
All-location, all-cause 28-day mortality (Study Day 29)	Secondary Outcome	Binary	Logistic regression model accounting for pre-specified baseline covariates
Survival through 28 days (Study Day 29)	Secondary Outcome	Time to event	Proportional hazards regression model accounting for pre-specified baseline covariates
Hospital discharge through 28 days (Study Day 29)	Secondary Outcome	Time to event	Proportional hazards regression model accounting for pre-specified baseline covariates; death treated as a competing risk
COVID Ordinal Outcomes Scale on Study Day 3	Secondary Outcome	Ordinal	Proportional odds model accounting for pre-specified baseline covariates

COVID Ordinal Outcomes Scale on Study Day 8	Secondary Outcome	Ordinal	Proportional odds model accounting for pre-specified baseline covariates
COVID Ordinal Outcomes Scale on Study Day 29	Secondary Outcome	Ordinal	Proportional odds model accounting for pre-specified baseline covariates
Composite of death or receipt of ECMO through Day 28	Secondary Outcome	Binary	Logistic regression model accounting for pre-specified baseline covariates
Oxygen-free days through Day 28	Secondary Outcome	Ordinal	Proportional odds model accounting for pre-specified baseline covariates
Ventilator-free days through Day 28	Secondary Outcome	Ordinal	Proportional odds model accounting for pre-specified baseline covariates
Vasopressor-free days through Day 28	Secondary Outcome	Ordinal	Proportional odds model accounting for pre-specified baseline covariates
ICU-free days through Day 28	Secondary Outcome	Ordinal	Proportional odds model accounting for pre-specified baseline covariates
Hospital-free days through Day 28	Secondary Outcome	Ordinal	Proportional odds model accounting for pre-specified baseline covariates
Seizure	Safety Outcome	Binary	Simple logistic regression

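### Randomisation is stratified by site, but site is in neither the primary nor the adjusted secondary models and no reason is given; the analysis is valid, and adding site is a minor, nearly free improvement

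*SAP*

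**What the plan says.** Both documents describe 1:1 randomisation in permuted blocks with site as the only stratification factor. Protocol 3.7: "Randomization will be completed in permuted blocks of varying size and stratified by site". SAP 4.4: "Randomization is completed in permuted blocks of varying size and stratified by site".

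The primary model does not carry that factor. Protocol 7.1 lists the covariates as "age, sex, baseline COVID Ordinal Outcome score, baseline SOFA score, and duration of acute respiratory infection symptoms prior to randomization". SAP 7.2 gives the same set: "Independent variables will include treatment group assignment and the following pre-specified 5 covariates". The result is to be reported as follows: "Results of the primary analysis of the primary outcome will be presented as an adjusted common odds ratio and associated 95% confidence intervals".

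The adjusted secondary models inherit the list. SAP 7.5 says of binary outcomes: "Binary secondary outcomes will be analyzed using multivariable logistic regression models with the same pre-specified covariates". The ordinal and time-to-event outcomes in that section use the same covariates, and the SAP Appendix A entry for the ordinal outcomes is "Proportional odds model accounting for pre-specified baseline covariates". SAP 7.4 also reuses the primary model's covariates in the interaction models. SAP 7.3 opens with "We will conduct two sensitivity analyses"; one drops patients without laboratory confirmation, the other drops patients who took no study drug, and neither adds site. Safety outcomes are unadjusted by design.

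Site does not appear in any of these models as a covariate, stratum or random effect, and no reason is given.

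**The concern.** Blocking within site forces the arms to be nearly balanced at each site. If sites differ in prognosis, that balance reduces the true variability of the treatment estimate. A model without site does not credit the reduction, so its standard error is a little too large under the null and the test is a little conservative. Some power for a real benefit or harm is left unused, although site is already held by the randomisation system.

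The odds ratio also changes meaning. Without site it is conditional on the five covariates only and lies closer to 1 than the odds ratio conditional on site as well. That is a different estimand, not bias, but the stopping limits of 1.1 and 0.70 are applied on that scale.

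Site differences beyond the five covariates are plausible, because Protocol 4.4 leaves other treatment to local clinicians. The documents do not show that they exist.

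**Working it through.** **1. Reproduce the plan's figures.** Inputs: 51 patients per arm per look, the Table 1 proportions 0.115 / 0.058 / 0.219 / 0.608, prior SD 0.352 for efficacy and a flat prior for futility (Protocol 7.1).

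Proportional odds information: V = nA·nB·N / [3(N+1)²] × (1 − Σp³) = 51·51·102 / (3·103²) × (1 − 0.237) = 8.336 × 0.763 = 6.36. So SE = 1/√6.36 = 0.397 at 102 patients.

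With SE_k = 0.40/√k at look k:
- Efficacy if z_k > 1.645·√(1 + SE_k²/0.352²): 2.49 at look 1 and 1.85 at look 5.
- Futility if z_k < ln(1.1)/SE_k − 1.282: −1.04 at look 1 and −0.75 at look 5.

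Over 1,000,000 simulated paths, efficacy/futility by the fifth look is 0.937/0.007 at OR 1.8 and about 0.060/0.384 at OR 1.0. Table 2 gives 0.937/0.007 and 0.061/0.383. The calculation reproduces and contains no site term.

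**2. Effect of omitting site.** Assumed, not in the documents: 34 unequal sites, blocks of 2/4/6, the split of Table 1 into seven levels, and one composite covariate (log OR 1 per SD) standing for the five. 510 patients were simulated, with 400 replicates at OR 1.8 and 1,000 at OR 1.0 for each SD.

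| Between-site SD (log odds) | 0.3 | 0.5 | 0.8 |
|---|---|---|---|
| Log OR, without / with site | 0.582 / 0.592 | 0.566 / 0.593 | 0.533 / 0.594 |
| SE, without / with site | 0.1666 / 0.1675 | 0.1662 / 0.1685 | 0.1656 / 0.1703 |
| Mean z at OR 1.8, ratio without : with | 0.989 | 0.968 | 0.925 |
| SD of z at OR 1.0, ratio without : with | 0.990 | 0.974 | 0.935 |

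The two ratios nearly coincide: 0.989/0.990 = 0.999, 0.968/0.974 = 0.994, 0.925/0.935 = 0.989. True signal-to-noise is therefore only 0.1 / 0.6 / 1.1% lower without site. The rest is calibration.

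**3. Put these ratios into the five-look rule.** OR 1.8 is taken as conditional on site, and the harm rule is left out, as in Table 2.

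| | With site | Without, SD 0.3 | SD 0.5 | SD 0.8 |
|---|---|---|---|---|
| Efficacy, OR 1.8 | 0.937 | 0.934 | 0.929 | 0.916 |
| Efficacy, OR 1.0 | 0.060 | 0.058 | 0.055 | 0.047 |
| Futility, OR 1.0 | 0.384 | 0.381 | 0.377 | 0.364 |
| Futility, OR 1.8 | 0.007 | 0.007 | 0.007 | 0.006 |

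The loss of efficacy at OR 1.8 is 0.3 / 0.8 / 2.1 points. If 1.8 and SE 0.40 are instead taken as belonging to the planned model itself, efficacy is 0.938 / 0.941 / 0.948 without site and 0.941 / 0.948 / 0.962 with it, so there is no fall below 0.937.

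Adding the harm rule at an assumed site-conditional OR of 1/1.8 = 0.556, the harm limit is crossed in 0.614 / 0.595 / 0.553 without site against 0.625 with it. Part of that gap is the scale to which 0.70 applies. Harm and futility stops together stay at 0.996 to 0.997.

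**4. Second, separately coded simulation.** Final look only, two-sided 5% test, 1,736 trials per scenario (Monte Carlo SE about 0.5 points for type I error and 0.8 for power), without against with a site intercept.

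| Sites, SD | Type I error, % | Power at OR 1.8, % |
|---|---|---|
| 34, SD 0 | 4.7 / 4.7 | 86.5 / 86.5 |
| 34, SD 0.3 | 5.3 / 5.7 | 86.4 / 86.6 |
| 34, SD 0.5 | 4.4 / 4.6 | 85.4 / 86.5 |
| 34, SD 0.8 | 3.7 / 4.6 | 81.9 / 84.9 |
| 15, SD 0.5 | 4.7 / 5.1 | 83.9 / 85.1 |
| 50, SD 0.5 | 4.8 / 5.0 | 83.6 / 84.4 |

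At SD 0.5 the loss is about 1 point with 15, 34 or 50 sites. One fixed effect per site is not a good alternative: across the scenarios run, type I error was about 5.1 to 6.4% and an OR of 1.8 was estimated at about 1.85 to 1.91.

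**The case against.** The strongest reply is that two valid analyses are being compared and the choice between them is a preference. Type I error is protected, the Protocol summary's claim of over 90% efficacy at OR 1.8 holds in every scenario, and at SD 0.3 to 0.5 the loss is under 1 point. Larger losses (about 5 points) need both the extreme SD of 0.8 and a smaller benefit such as OR 1.3, which the documents do not use. The gain is also mostly a trade: the planned model's false-efficacy rate of 0.058 / 0.055 / 0.047 goes back to about 0.060. A site-adjusted sensitivity analysis, or a sentence explaining the omission, might be enough.

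Most of this stands, and it is why the point is minor. It does not remove the point. The rate of 0.060 is within the 0.061 that the protocol already accepts, so nothing that was promised is given up. If sites do not differ, including site costs almost nothing (SE 0.1671 against 0.1668).

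A reader might infer that leaving out a stratification factor invalidates the test, biases the odds ratio or leaves the trial underpowered. The documents support none of these. The error runs towards conservatism, the smaller odds ratio is a different estimand, and the stated operating characteristics hold. Nor does the conservatism carry over to the futility rule, which changes little.

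**Conclusion.** The omission is real and unexplained, and its consequence is small. The planned analysis is valid and misses no stated figure. If sites differ beyond the five covariates, it is mildly conservative for claiming benefit or harm: 0.3 to 0.8 points of five-look efficacy at OR 1.8 for a between-site SD of 0.3 to 0.5, and 2.1 points at 0.8. Most of what a site term returns is calibration rather than new information.

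These sizes rest on an assumed site count (34, with 15 and 50 tried at SD 0.5), assumed SDs, block sizes and site sizes, and a single composite covariate. The direction follows from the design; the size would change with these inputs. Rated minor, as a nearly free improvement.

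**What to change.** Settle the following before unblinding.

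- **Primary model:** add a random intercept for site, keeping the five covariates, in both Protocol 7.1 and SAP 7.2. Changing only the SAP would leave the two documents in disagreement. State that the odds ratio is conditional on site and the five covariates.
- **Other models:** use the same form at the interim analyses (SAP 4.3), in the effect-modification models (SAP 7.4) and for the ordinal and binary secondary outcomes (SAP 7.5 and Appendix A). For the adjusted time-to-event models, either account for site (for example by a frailty or stratification) or state that they are not adjusted for it. The unadjusted safety models are unaffected.
- **Fallback and sensitivity analysis:** name the five-covariate model as the fallback if a fit does not converge, report any look at which it was used, and add it to SAP 7.3 as a sensitivity analysis.
- **DSMB:** SAP 4.3 says that it approved the stopping criteria. Tell it that the model behind them gains a site term, that the scale to which 1.1 and 0.70 apply shifts slightly, and that some conservatism is given up.

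**Cost:** a protocol and SAP amendment and a slightly more complex model, with no extra patients or data. Little is gained early or if sites do not differ: at the first look, with 34 sites, the estimated site SD was below 0.1 in 46% / 32% / 10% of simulated trials at true SD 0.3 / 0.5 / 0.8. For 14-day mortality the gain is smaller still (ratio of mean z 0.997 / 0.993 / 0.979). The fallback should rarely be needed: there was no convergence failure in 6,100 ordinal or 3,000 mortality fits.

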7.3 Sensitivity Analyses of the Primary Outcome

We will conduct two sensitivity analyses:

1. **Exclusion of SARS-CoV-2 negative patients.** The primary analysis included all enrolled patients enrolled in the trial. Given delays in SARS-CoV-2 testing early in the pandemic, the trial eligibility criteria initially allowed enrollment of hospitalized patients with suspected or confirmed SARS-CoV-2 infection. As testing capabilities improved, the inclusion criteria were narrowed on April 21, 2020 (after 18 days of enrollment and inclusion of 2 patients without laboratory-confirmed COVID-19) to include only laboratory-confirmed cases. To determine whether the results of the primary analysis of the primary outcome were affected by enrollment of patients who subsequently tested negative for SARS-CoV-2, in this sensitivity analysis the primary analysis will be repeated in the subset of patients with a positive test for SARS-CoV-2 (i.e., excluding patients without laboratory-confirmed SARS-CoV-2).
2. **Modified intention-to-treat.** The primary analysis will be repeated among the subset of patients who received at least one dose of study drug (excluding patients who received no doses of study drug).

